#### 4. Inclusion/Exclusion Criteria

Inclusion Criteria: Participants must be clinically diagnosed with svPPA, nfvPPA or lvPPA, unclassifiable PPA, or MCI. Diagnosis will be based on neuropsychological testing, language testing (most commonly the Western Aphasia Battery), MRI and clinical assessment. They must also be right-handed, speakers of English and have up to high-school education. Participants will be recruited from the [name] PPA database, one of the largest in the country or from [name] clinic or may be referred by other clinicians with a confirmed diagnosis of PPA or MCI. The age range of the participants will be 50-90 years old due to variability inherent in this neurodegenerative syndrome.

Exclusion Criteria: Potential participants will be excluded if they have uncorrected visual or hearing impairment by self report or stroke/other premorbid neurological or psychiatric disorder affecting the brain, or any other language-based learning disorder other than PPA. Potential participants will also be excluded from the spelling treatment if they were not premorbidly proficient spellers. Furthermore, participants in advanced stages of the disease will be excluded since it has been shown that at these stages most

language functions are very impaired (Sepelyak et al., 2011) and it will be difficult to see any results specific to the current therapeutic intervention. Furthermore, participants with pre-existing psychiatric disorders such as behavioral disturbances, severe depression, schizophrenia that do not allow them to comply or follow the study schedule and requirements such as repeated evaluation and therapy will be excluded. In addition, individuals with severe claustrophobia and cardiac pacemakers or ferromagnetic implants will be excluded from the MRI portion of the study since they may not tolerate the MRS sessions. Pregnant women will also be excluded. However, they could still participate in the treatment study without having the MRI scans.

Inclusion/Exclusion Criteria for Healthy Controls: For the behavioral assessment, actigraphy, and imaging (volumetric, connectivity and MRS analyses) portions of the study, we will need to compare our PPA patients to an age- and education-matched control group. Therefore, we will recruit a group of 30 participants, mostly from the pool of spouses of our tDCS study participants or matched controls from the Johns Hopkins community. Healthy controls must be right-handed, 50-85 years old, speakers of English, and have at least high-school education and no neurological history outlined in the exclusion criteria above, including stroke, TIA, neurodegenerative disease, neurodevelopmental disorder, and TBI.

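### The education limits for patients and for education-matched healthy controls run in opposite directions and meet only at exactly high school; Section 4 must be reconciled

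*Combined protocol and SAP*

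**What the plan says.** All the relevant text is in Section 4 of the combined protocol and SAP, Inclusion/Exclusion Criteria.

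- **Patients, education:** they must "have up to high-school education".
- **Patients, age:** "The age range of the participants will be 50-90 years old".
- **Healthy controls, education:** they must "have at least high-school education and no neurological history outlined in the exclusion criteria above". Their age range is 50 to 85.
- **Purpose of the controls:** "For the behavioral assessment, actigraphy, and imaging (volumetric, connectivity and MRS analyses) portions of the study", the plan states that "we will need to compare our PPA patients to an age- and education-matched control group".

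The control group numbers 30 and is to come mostly from participants' spouses, or otherwise from matched people in the institution's community. Section 3a (study design) also calls the controls matched, and says that they are assessed once and may take part in any portion they choose.

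**The concern.** A ceiling for one group and a floor for the other cannot produce a group matched on education, except at the point where the two limits touch. If recruitment follows the text, no control can have less education than any patient. A difference in language scores, cognition, activity, sleep or imaging could then reflect schooling as well as disease.

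Nothing later in the plan repairs this. Section 6c mentions regression only to see whether tDCS effects vary with patient characteristics, and gives age and atrophy volume as examples. No adjustment for education is planned anywhere.

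The patient criterion also matters apart from the controls. Read literally, it decides who enters the treatment study and shuts out anyone with education beyond high school. That bears on recruitment and on the population to which the results apply.

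**Working it through.** **1. The plan's own figure, and whether this point touches it.** The only power figure is in Section 6c: 30 participants, design effect 1.5, effect size 0.8, power 75%. Alpha is not stated; I assume 0.05 two-sided.

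- Equivalent independent sample: 30 × 1.5 = 45, or 22.5 per arm.
- Normal approximation: 0.8 × √(22.5/2) = 2.683; 2.683 − 1.960 = 0.723; power = Φ(0.723) = 76.5%.
- Noncentral t: 74.6%.

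Both agree with 75% (a one-sided test would give 85.0%). The calculation concerns tDCS against sham in the crossover and uses no healthy controls, so the education criteria do not enter it. The documents give no power or sample-size figure for the patient-control comparisons.

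**2. The criteria side by side.**

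| | Patients | Healthy controls |
|---|---|---|
| Education | high school or below | high school or above |
| Age | 50–90 | 50–85 |

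- Education: the intersection is one level, exactly high school. A patient below it has no eligible control at the same level. A control above it has no eligible patient at the same level.
- Age: the control range lies inside the patient range. Patients aged 86–90 have no control of the same age, but the groups overlap over 50–85.
- Spouses: a spouse below high school is ineligible as a control. A spouse above high school is eligible but not matched on education to any patient who meets the ceiling.

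**3. How far the groups separate.** Let a be the share of patients, and b the share of controls, at exactly high school. A randomly drawn control fails to be strictly more educated than a randomly drawn patient only if both are at that level. Hence P(control more educated) = 1 − ab. The documents give neither share; with assumed values:

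| a | b | 1 − ab |
|---|---|---|
| 1 | 1 | 0 |
| 0.5 | 0.5 | 0.75 |
| 0.5 | 0.2 | 0.90 |
| 0.2 | 0.2 | 0.96 |

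**4. Possible consequence, by assumption only.** Suppose a 4-year gap in education and 0.05 to 0.15 SD per year on a language test. Then 4 × 0.05 = 0.2 SD and 4 × 0.15 = 0.6 SD. None of these inputs is in the documents, and no rate is offered for actigraphy or imaging.

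With an assumed 30 patients against the 30 controls, no disease effect and a two-sided 5% test, the standard error is √(2/30) = 0.258 SD. The rejection rate for a shift d is 1 − Φ(1.960 − d/0.258) + Φ(−1.960 − d/0.258):

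| Assumed shift d (SD) | False-positive rate |
|---|---|
| 0 | 5% |
| 0.2 | 12% |
| 0.3 | 21% |
| 0.5 | 49% |
| 0.8 | 87% |

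These rates show how sensitive a 30-against-30 comparison would be to such a shift. They do not estimate what will happen in this study.

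**The case against.** Four points can fairly be made on the other side.

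- **It may be a drafting slip.** Nothing presents opposite limits as deliberate, and the stated intent is the reverse. If one of the two phrases is an error, the defect is contradictory text and not actual confounding. The documents do not settle this. The contradiction stands either way, because staff screen against the text as written.
- **Matching may rescue the comparison.** A reader might infer that education is confounded with disease in every patient-control comparison. The documents do not support that: the ranges share the high-school level, and if the promised matching were enforced there, comparisons at that level would be free of this confounding. The price would be to leave out everyone else.
- **The controls are peripheral to the trial's main question.** They appear in no objective or hypothesis, in neither the primary nor the secondary outcomes (Sections 6a and 6b), and not in the statistical plan (Section 6c). A reader might infer a threat to the treatment result. There is none to its internal validity: Section 3e has each patient undergo both active and sham conditions.
- **The age limits are not a contradiction.** It is tempting to say that patients aged 86–90 cannot be matched. That presumes individual matching, which Section 4 does not specify. A group of controls aged 50–85 can still be matched to the patients at group level.

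These points limit the reach of the problem. They do not remove the conflict between the two education criteria and the stated matching.

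**Conclusion.** The eligibility text is wrong as written. The two education criteria contradict the education matching promised in the same section, and no other part of the document resolves it. Applied literally, they overlap at one level only, exclude every patient educated beyond high school, and confound education with disease in the behavioral, actigraphy and imaging comparisons outside that level.

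The conflict of wording is certain. The size of any resulting bias is not known, since it depends on how recruitment is actually done and on education effects that the documents do not give. The 0.2 to 0.6 SD range and the false-positive rates above rest wholly on assumed inputs and should not be quoted as findings. The within-patient tDCS-versus-sham comparison and its stated power are unaffected; for the treatment study, the literal criterion limits only who can enter and to whom the results apply.

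**What to change.** 1. Reconcile the patient and healthy-control paragraphs of Section 4 so that one education criterion applies to both groups. The documents do not show which wording was intended, so the sponsor must decide.
2. Give both groups the same upper age limit, or state that age is matched at group level.
3. Once the education ranges overlap, add a sentence that patient-control comparisons will be adjusted for age and years of education. This is a useful addition but no substitute for the first step: under the present limits the groups share one education level, and a regression adjustment would rest on extrapolation.

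The cost is a wording amendment to the eligibility criteria and one added sentence on analysis. No further participants are needed.

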## 5. Drugs/ Substances/ Devices

*a.* The rationale for choosing the drug and dose or for choosing the device to be used.

tDCS has been established as a valid and reliable tool for at least temporarily affecting brain and behavior with minimal risks. Stimulation will be delivered by a battery-driven constant current stimulator (Chattanooga lonto Device, Soterix 1x1 CT: clinical trials, Neuroelectrics Starstim 8 or Soterix mini-CT remote device or YBrain inc remote device). The stimulator is not connected to a mainline power source and cannot produce in excess of 4mA of current. In the case of remote stimulation, current is pre-determined and cannot be altered by participants (a distinct password is required). We will use non-metallic, conductive rubber electrodes covered by saline-soaked sponges to minimize the potential for chemical reactions at the interface of the scalp or skin and the electrodes.

We may also provide willing participants with accelerometers, i.e. small portable (at the wrist or ankle) devices that measure activity and sleep patterns or portable touch-screen devices. The accelerometers will be worn during the daily intervention periods, i.e., for 2-3 weeks in each period of every day visits for tDCS plus speech therapy or sham plus speech therapy. The portable touch-screens devices will be used for the participants who will opt for the booster training we are offering as an additional way to maximize their involvement and training.

- *b.* Justification and safety information if FDA approved drugs will be administered for non-FDA approved indications or if doses or routes of administration or participant populations are changed. N/A
- *c.* Justification and safety information if non-FDA approved drugs without an IND will be administered. N/A

#### 6. Study Statistics

#### *a. Primary outcome variable.*

The primary outcome measures will be: a) change in performance from pre- to post-treatment levels on the trained items (e.g. change in % accuracy in phoneme-grapheme conversion of trained phonemes, % accuracy naming of trained pictures, average % correct names produced in trained categories in 1 minute), and, b) generalization to untrained items, measured by change in performance from pre- to post-treatment levels on the trained items (e.g. change in % accuracy in phoneme-grapheme conversion of untrained phonemes, % accuracy naming of untrained pictures, average % correct names produced in untrained categories in 1 minute). For those individuals with DLPFC stimulation for executive functions, we will use an additional automated score from BrainHQ program training (Smith et al., 2009). For individuals

receiving home-based tDCS over the left perisylvian areas and their right hemisphere homologs, we will assess pre- to post- language scores.

# b. Secondary outcome variables.

Secondary outcome variables will be generalization of the improvement induced by the stimulation of IFG and SMG in other language and cognitive functions with the same neural substrates. Therefore improvement may generalize to verbal working memory tasks such as sentence repetition and single digit span backward and forward but will not generalize to functions that do not involve IFG, and SMG, such as picture association.

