
Although we do not know the exact mechanisms by which tDCS works, it has been claimed that the low current applied on the scalp has the potential to alter synaptic excitability at the stimulation area (Nitsche et al., 2004; Stagg & Nitsche, 2011). We therefore hypothesize that effects of generalization to other functions will depend on the area stimulated. In the existing literature effects of tDCS in the areas stimulated have been correlated with the cognitive functions subserved by these areas. Furthermore, it has been shown that stimulation of specific areas affects only functions subserved by these areas but not others; Ferrucci and colleagues (2008) have shown that stimulation of the temporo-parietal junction affected word recognition but not visual attention which was subserved by different areas. There is only one other study that has looked at transfer of treatment effects to other language functions. (Marangolo et al., 2011)) have shown that beneficial effects from syllable production training in combination with stimulation at the left inferior frontal gyrus (IFG) of patients with stroke transferred to other production tasks such as word repetition and reading. In the present study we will test the hypothesis that spelling therapy gains will not only generalize to the spelling of untrained items but also to other language and cognitive functions that are subserved by the stimulated areas. In the same logic, we do not expect generalization to language and cognitive functions that have neural substrates different from the stimulated areas.

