#### Language Tasks:

Patients will be administered baseline language and cognitive tasks, including 1 or more of the following, depending on their residual language and cognitive skills: a) writing to dictation b) oral spelling c) oral and written naming of pictures d) word-picture matching f) written picture description g) digit span h) spatial span i) verbal learning

Language Therapy tasks:

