## c. Statistical plan including sample size justification and interim data analysis.

Design. This is a crossover trial, where each participant will be randomly assigned to receive either "IFG tDCS, then sham then SMG (in case a second stimulation site is implemented)" (group1) or "SMG then sham then IFG" or "sham then IFG then SMG". In case a second stimulation site is not implemented participants will receive either sham and then tDCS (group 1) or tDCS and then sham (group 2). Based on previous studies regarding long-term effects of tDCS (see Fiori et al., 2011; Fridriksson et al., 2011; both looking at 3-weeks post-stimulation in participants with aphasia) and given the degenerative nature of PPA (and some cases of MCI), we assume that even though the effect of tDCS on the absolute level of the outcome may or may not persist at 2 weeks, the effect on the rate of decline persists no longer than 2 weeks. Analyses. The primary analyses will be a robust type of repeated measures Multivariate ANCOVA. Specifically, for each subject (i) and at follow-up times t=immediately after treatment, then 2 weeks and 2 months, we will consider the data  $IFG_{ti}$ ,  $SMG_{ti}$ , and  $S_{ti}$ ; here,  $IFG_{ti}$  is the change of outcome from just before IFG tDCS treatment to time t after IFG tDCS treatment for subject i; and similarly for SMGt,i, and St,i for IFG tDCS and sham. For the behavioral methods, change of outcome is considered the difference (before and after therapy) of the independent measure of initial letter-sound associations learned. Then the research hypothesis that IFG (or SMG) treatment is superior to sham will be tested by testing the hypotheses that the distribution  $pr(R_{ij} - S_{t,i})$  (or  $pr(L_{t,i} - S_{t,i})$ ) is not centered at zero. This will be done nonparametrically by obtaining the latter null distributions by the random permutation of the treatment labels (IFG, S, SMG) of the data for each patient (Rosenbaum, 1988). The design effect, i.e., the ratio of sample sizes needed by an independence design vs. the crossover design to achieve a given power, depends on the correlations of outcomes across times and treatments. We have calculated that this crossover design with 30 participants and design effect of 1.5 has power 75% to detect an effect size of 0.8 between a tDCS site and sham treatment. In secondary analysis, we will use regression to examine if any effects of tDCS vary across participants with different characteristics such as age and atrophy volume. The present design allows us to evaluate the language and neuromodulatory effects of both IFG and SMG stimulation as well as language therapy alone (in the condition of sham stimulation).

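### The plan predicts no generalisation to functions outside IFG and SMG, but its only treatment test looks for a difference from zero and cannot support a prediction of no effect

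*Combined protocol and SAP*

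**What the plan says.** Section 6b lists generalisation to other functions as the secondary outcome. It names sentence repetition and digit span as tasks that may improve, and then predicts that improvement "will not generalize to functions that do not involve IFG, and SMG, such as picture association". Section 2 (Background) makes the same prediction: "we do not expect generalization to language and cognitive functions that have neural substrates different from the stimulated areas".

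Section 6c describes one test of treatment: whether the distribution of the within-patient difference between active stimulation and sham is centred away from zero. On the null distribution it says: "This will be done nonparametrically by obtaining the latter null distributions by the random permutation of the treatment labels". The one secondary analysis it names concerns effect modifiers: "we will use regression to examine if any effects of tDCS vary across participants with different characteristics such as age and atrophy volume". The power statement is that "this crossover design with 30 participants and design effect of 1.5 has power 75% to detect an effect size of 0.8".

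The plan gives no margin, no interval rule, no comparison of related with unrelated tasks, and no power for the prediction of no generalisation. It also states no significance level or sidedness.

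**The concern.** The prediction has a positive half (tasks served by the stimulated areas may improve) and a negative half (other tasks will not). A difference-from-zero test can support the positive half. For the negative half it can only fail to reject, and in a trial of this size that happens often when a real effect exists.

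Anyone following the plan as written would have only a non-significant picture-association result to set against the prediction. Placing that beside a significant result on repetition or digit span does not test whether the two effects differ. At stake is the mechanistic conclusion that tDCS effects follow the stimulated region, on which section 2 builds its reasoning about generalisation. The primary outcome is not affected.

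**Working it through.** **Inputs from the plan (section 6c).** 30 crossover participants, design effect 1.5, effect size 0.8 (taken as SD units), power 75%. The design effect is defined as "the ratio of sample sizes needed by an independence design vs. the crossover design to achieve a given power", so a value of 1.5 means that 30 crossover participants carry the information of 30 × 1.5 = 45 independent participants, or 22.5 per arm.

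**Assumptions, because the plan is silent.** Two-sided 5% level; no dropout; all 30 participants scored on picture association; the same design effect of 1.5 for that task. A two-sample t calculation stands in for the permutation test.

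**Step 1: reproduce the plan's figure.** The noncentrality is d × √(n/2) = 0.8 × √11.25 = 2.68 on 2 × 22.5 − 2 = 43 degrees of freedom. Power is 74.6% (76.5% by normal approximation), which agrees with the stated 75%. A one-sided 5% test would give 84.0%, so the two-sided level is the one that fits.

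**Step 2: chance of missing a real effect on the unrelated task.** The formula is the same, with a different d. The documents give no expected effect on unrelated tasks, so a range is shown.

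| True effect (SD) | Noncentrality | Power | Non-significant |
|---|---|---|---|
| 0.4 | 1.34 | 26% | 74% |
| 0.5 | 1.68 | 37% | 63% |
| 0.6 | 2.01 | 50% | 50% |
| 0.8 | 2.68 | 75% | 25% |

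A miss is the more likely result only below about 0.6 SD.

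**Step 3: what an observed zero would exclude.** The standard error is √(2/22.5) = 0.298 SD. The 95% half-width is 2.017 × 0.298 = 0.60 SD, so an estimate of exactly zero remains compatible with effects up to about 0.6 SD in either direction.

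**Step 4: could absence be shown with a margin?** Two one-sided 5% tests require the 90% interval to lie inside the margin. Its half-width is 1.681 × 0.298 = 0.50 SD (0.49 by normal approximation). No margin below about 0.5 SD can be met, even with an observed difference of zero. A margin of 0.8 SD would be met about 70% of the time if the true difference is zero, but 0.8 SD is the full effect that the trial is sized to detect, so meeting it would not amount to no generalisation.

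**Step 5: power of a direct contrast between tasks.** If the two tasks' effects have correlation r and equal variance, the SD of their difference is √(2(1 − r)) times that of one effect. For a true difference of 0.8 SD:

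- r = 0: 0.8/1.414 = 0.566, power 46%
- r = 0.3: 0.8/1.183 = 0.676, power 60%
- r = 0.5: 0.8/1.000 = 0.800, power 75%

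The correlations are assumptions. For a difference of 0.5 SD, power falls to 21%, 28% and 37%.

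**The case against.** The strongest reply is that the plan never says it will read non-significance as proof. Section 6b states an expectation within a list of outcomes, section 2 says only what is expected, and Hypothesis 1c contains positive predictions only. This stands. A reader might infer that the investigators intend to declare specificity from a significant result on one set of tasks and a non-significant result on the other. The documents contain no such rule, and what a future report would claim is conjecture. What remains is that the prediction appears among the secondary outcomes and the only treatment test supplied cannot support it.

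A second reply is that the trial would not usually miss a real effect. That is right above about 0.6 SD; at 0.8 SD the miss rate is 25%.

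A third is that the figures borrow from the primary comparison. That also stands. Section 6c says the design effect depends on correlations across times and treatments, and nothing shows that 1.5 applies to picture association. Precision could also be lower: section 3 (Language Tasks) gives baseline tasks "including 1 or more of the following, depending on their residual language and cognitive skills", and its list does not include picture association, so fewer than 30 participants may have a score.

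A fourth is that a contrast between tasks does not establish absence. True effects of 0.9 SD on related tasks and 0.3 SD on picture association, for example, would differ while both being real. A reader might infer that the contrast makes an equivalence margin unnecessary. It does so only for a claim of differential effect; a claim that gains do not generalise would still need a margin.

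**Conclusion.** The point holds as a mismatch between a stated prediction and the available test. The plan predicts no effect on functions outside IFG and SMG and provides only a test of difference from zero. The sizes in steps 2 and 3 rest on the two-sided 5% level, the design effect of 1.5 carrying over to picture association, and complete data on 30 participants. Incomplete testing would widen the interval and raise the miss rates.

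The documents do not support saying that the plan adopts an invalid decision rule, or that real effects of every size would usually be missed. The issue is minor: it concerns one secondary prediction and leaves the primary outcome and the sample size unchanged.

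**What to change.** In sections 6b and 6c:

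- Name picture association as the control task, and list the IFG/SMG tasks that form the comparison.
- Pre-specify one within-person contrast on standardised scores, in participants with both scores: (tDCS minus sham change on the named IFG/SMG tasks) minus (tDCS minus sham change on picture association). State how the related tasks are combined and which SD standardises each score.
- Claim a differential, site-related effect only if the interval for this contrast excludes zero.
- Report the picture-association effect with its interval, and do not conclude absence of generalisation from a non-significant result. A claim of absence would need a margin stated in advance, and 30 participants could not meet one below about 0.5 SD.

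The cost is one added contrast on outcomes that the prediction already requires, plus making sure that picture association is given to as many participants as possible. The downside is noise: on the figures in step 5 the contrast will often be inconclusive, so a specificity claim becomes harder to reach.
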